Appendix 3. Charlson Co-Morbidity Index

Table 1. Charlson Comorbidity Index Scoring System

Score	Condition
1	Myocardial infarction (history, not ECG changes only) Congestive heart failure Peripheral vascular disease (includes aortic aneurysm ≥ 6 cm) Cerebrovascular disease: CVA with mild or no residua or TIA Dementia Chronic pulmonary disease Connective tissue disease Peptic ulcer disease Mild liver disease (without portal hypertension, includes chronic hepatitis) Diabetes without end-organ damage (excludes diet-controlled alone)
2	Hemiplegia Moderate or severe renal disease Diabetes with end-organ damage (retinopathy, neuropathy, nephropathy, or brittle diabetes) Tumor without metastases (exclude if >5 y from diagnosis) Leukemia (acute or chronic) Lymphoma
3	Moderate or severe liver disease
6	Metastatic solid tumor AIDS (not just HIV positive)

NOTE. For each decade > 40 years of age, a score of 1 is added to the above score.

Abbreviations: ECG, electrocardiogram; CVA, cerebrovascular accident; TIA, transient ischemic attack; AIDS, acquired immunodeficiency syndrome; HIV, human immunodeficiency virus.

Appendix 4: Bioelectrical Impedance Device for Assessment of Percentage Body Fat

ImpediMed DF50

Instruction Manual Link:

<http://www.impedimed.com/products/df50/df50-for-usa.htm>

Appendix 5: Accelerometer For Ambulatory Recording of Activity Levels

Actigraph GT3X+ Accelerometer

Accelerometer Participant Instructions

- Please wear the belt with the accelerometer for seven days, starting the morning of _____ and ending the evening of _____.
- Wear the belt around your waist with the accelerometer placed on your right side. The device should be attached securely to your body so it does not have any extraneous movement.
- Please wear the belt with the accelerometer at all times when awake, from rising in the morning until going to sleep at night, for seven consecutive days.
- The device is **NOT** waterproof – remove the belt when bathing or swimming.
- Please return the belt with the accelerometer in person, or via USPS in the provided addressed stamped envelope, as soon as possible after completing your seven days.
- If any questions, please contact us via email or telephone: [name] at [contact] or [contact].

Appendix 6. Data and Safety Monitoring Plan for a Phase 2 Institutional Study

The UCSF Helen Diller Family Comprehensive Cancer Center (HDFCCC) Data and Safety Monitoring Committee (DSMC) is responsible for monitoring data quality and subject safety for all HDFCCC institutional clinical studies. A summary of DSMC activities for this study include:

- Review of Grade 2 and higher adverse events.
- Review of suspected adverse reactions considered "serious".

Monitoring and Reporting Guidelines

Investigators will conduct continuous review of data and subject safety and discuss each subject's treatment at monthly Site Committee meetings. These discussions are documented in the Site Committee meeting minutes. The discussion will include the number of subjects, significant toxicities in accordance with the protocol, and observed responses.

Adverse Event Review and Monitoring

All grade(s) 3-5 adverse events, whether or not unexpected, and whether or not considered to be associated with the use of the study treatment, will be entered into OnCore®, UCSF's Clinical Trial Management System.

All grade(s) 3-5 adverse events entered into OnCore® will be reviewed on a monthly basis at the Site Committee meetings. The Site Committee will review and discuss the selected toxicity, the toxicity grade, and the attribution of relationship of the adverse event to the administration of the study treatment.

In addition, all suspected adverse reactions considered "serious" entered into OnCore®, will be reviewed and monitored by the Data and Safety Monitoring Committee on an ongoing basis and discussed at DSMC meetings, which take place every six weeks.

If a death occurs during the treatment phase of the study or within 30 days after the last administration of the study treatment and it is determined to be related either to the study treatment or to a study procedure, the Investigator or his/her designee must notify the DSMC Chair within **1 business day** of knowledge of this event. The contact may be by phone or e-mail.

Increase in Adverse Event Rates

[figure not shown]
If an increase in the frequency of Grade 3 or 4 adverse events (above the rate reported in the Investigator Brochure or package insert) is noted in the study, a report should be submitted to the DSMC at the time the increased rate is identified. The report will indicate if the incidence of adverse events observed in the study is above the range stated in the Investigator Brochure or package insert.

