4.1 Inclusion Criteria

- Histologic confirmation of adenocarcinoma of the prostate
- Receiving or planning to receive ADT with LHRH agonist or antagonist
- Expected duration of ADT at least 12 months from date of study consent
- Concurrent antiandrogen therapy allowed but not required
- First dose of LHRH agonist or antagonist no more than 6 months prior to date of study consent
- Prior/concurrent radiation allowed
- Other investigational agents in addition to LHRH agonist/antagonist are allowed (e.g. novel anti-androgens, androgen synthesis inhibitors)
- Prior androgen deprivation therapy allowed, provided there is documented evidence of testosterone recovery to > 150 ng/dL and greater than 12 months duration between last “effective” date of ADT and date of study consent
- **Randomized cohort only:**
 - No prior chemotherapy within 12 months of start date of study
 - No planned chemotherapy at least 12 months from study entry
- **Non-randomized pilot cohort:**
 - Concurrent chemotherapy (initiated within 3 months of study entry) or planned chemotherapy within 3 months of study entry
- ECOG performance status of 0 – 2
- Ability to sign written informed consent
- Willing to attend monthly clinic visits at UCSF

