6.1.3 Drug Supply

The drugs will be commercially supplied.

For a complete description of these drugs, please see the package inserts.

7. Study Activities

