7.5 Day 1 and Monthly Study Visits (+/- 2 weeks)

Patients randomized to the STAND clinic will return to clinic on a monthly basis. During the course of these monthly visits, there will be a series of self-guided educational modules discussing various aspects of androgen deprivation therapy and management of side effects.

These modules will be comprised of PowerPoint slide presentations which the patients will view on a self-directed manner during their clinic visit, with the opportunity to ask questions before and after the presentation. In addition, on a rotating schedule, patients will meet one-to-one with a licensed exercise trainer, registered dietitian, and symptom management service to receive individualized counseling. The rotation of the schedule of providers may be adjusted depending upon availability of provider and patient. In total, patients will meet with each specialized service four times on a rotating every 3 month-schedule.

Patients enrolled in the non-randomized chemohormonal cohort will return to clinic on an approximately monthly basis for rotating visits with exercise, nutrition, and symptom management, with schedule of visits matching whenever possible the scheduled dates of infusion center appointments

Patients randomized to the standard-of-care arm will be referred to nutrition, exercise, and symptom management service upon patient request or if deemed necessary by health care provider, as per current standard-of-care and practice guidelines. Patients will have the opportunity to receive the educational modules for review outside the clinic setting

During the course of the visit with the exercise trainer, patients will review exercise patterns with the use of questionnaires filled out prior to visit and via the use of ambulatory accelerometer which quantifies activity level. Patients will receive individualized counseling regarding specific exercises, and reinforcement of establishing regular exercise routine. During the course of the visit, patients will have the opportunity to practice actual exercise routines under the supervision of the exercise trainer, and will receive in-person assessment of aerobic fitness level.

During the course of the visit with the registered dietitian, patients will review dietary habits with the use of diet logs filled out prior to each visit. Patients will receive individualized counseling on recommended foods/diet, and will receive feedback on progress on a longitudinal basis.

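### The adverse-event rate trigger in Appendix 6 is benchmarked to drug labelling and not split by arm, so it is not designed to detect harm from the randomised STAND intervention

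*Combined protocol and SAP*

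**What the plan says.** **The trigger.** Under Increase in Adverse Event Rates, Appendix 6 sets this condition: "If an increase in the frequency of Grade 3 or 4 adverse events (above the rate reported in the Investigator Brochure or package insert"). The consequence, once someone recognises such a rise, is a DSMC report. The rule names no product, rate or margin, and no arm or cohort.

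**The attribution rule.** For Grade 3-5 events, the Site Committee considers "the attribution of relationship of the adverse event to the administration of the study treatment". The term for the treatment is not defined there. The clause on related deaths also covers study procedures. The attribution and rate clauses do not.

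**The products described.** Sections 5 and 6 describe only LHRH analogues. Section 6.1.3 says "The drugs will be commercially supplied" and "For a complete description of these drugs, please see the package inserts". Section 9.1 gives LHRH injections to both arms.

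**The randomised contrast.** STAND adds monthly educational modules and rotating exercise, nutrition and symptom-management sessions. In the exercise sessions "patients will have the opportunity to practice actual exercise routines under the supervision of the exercise trainer" (Section 7.5).

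**Other exposures.** The pilot cohort enters with "Concurrent chemotherapy (initiated within 3 months of study entry) or planned chemotherapy within 3 months of study entry" (Section 4.1). The same section says: "Other investigational agents in addition to LHRH agonist/antagonist are allowed (e.g. novel anti-androgens, androgen synthesis inhibitors").

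**Other monitoring in Appendix 6.** The DSMC's listed activities include review of Grade 2 and higher events and of serious suspected reactions. All Grade 3-5 events are entered whatever their attribution and reviewed monthly by the Site Committee.

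Neither Appendix 6 nor Section 9 specifies an adverse-event comparison by arm or cohort.

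**The concern.** Appendix 6 reads as though a drug were under test, but the drug is common to both arms. What differs by randomisation is exercise, diet and symptom management, and no external document gives an expected adverse-event rate for that package. A trigger of this kind asks whether the study as a whole looks worse than a label. It does not ask whether STAND men fare worse than usual-care men.

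The protocol itself names fracture and cardiovascular risk under androgen deprivation (Sections 1.1 and 1.2.3). A fracture or cardiac event connected with exercise would look like background toxicity, and the natural way to tell the two apart is the concurrent control arm. Usual-care men are offered STAND at month 12 (Section 7.9), and a favourable result is meant to justify a larger trial (Section 2.1). An arm-specific view of severe events therefore has a use both during and after the study.

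**Working it through.** The plan gives no numerical figure for the trigger, so there is none to reproduce. The denominators come from Section 9.2: 40 men per randomised arm and 20 in the pilot cohort. All event rates below are assumptions, because the documents give none.

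**Set-up.** Let L be the label rate, taken as the proportion of men with at least one Grade 3-4 event. The trigger is read as firing when the pooled observed proportion exceeds L. Probabilities are exact sums of independent binomials at one look with all men counted. Repeated looks would raise every probability.

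**1. Randomised men only.** Let usual care run at bL and STAND at r times that. The expected pooled rate is

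(bL + r·bL)/2 = L·b(1 + r)/2,

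which exceeds L only if r > 2/b − 1.

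- b = 1: any r above 1 is enough.
- b = 0.7: r must exceed 2/0.7 − 1 = 1.86.
- b = 0.5: r must exceed 2/0.5 − 1 = 3.

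So with background at half the label rate, a doubling gives an expected pooled rate of 0.75L, still below the threshold.

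| Probability the trigger fires (40 + 40) | L = 5% | 10% | 20% | 30% |
|---|---|---|---|---|
| Both arms at L, no harm | 0.37 | 0.41 | 0.43 | 0.45 |
| Usual care at L, STAND doubled | 0.73 | 0.87 | 0.97 | 1.00 |
| Usual care at 0.7L, STAND doubled | 0.41 | 0.47 | 0.52 | 0.56 |
| Usual care at 0.5L, STAND doubled | 0.18 | 0.14 | 0.08 | 0.04 |

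The same doubling is nearly always flagged or nearly always missed, depending on where background sits relative to a label. The first row is high because no margin is set.

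**2. Adding the 20 pilot men, with no STAND effect.** With chemotherapy-cohort rate c, the expected pooled rate is 0.8·bL + 0.2·c. This exceeds L when c > L if b = 1, and when c > (1 − 0.4)L/0.2 = 3L if b = 0.5.

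| Probability the trigger fires (80 + 20) | c = 30% | 50% | 70% |
|---|---|---|---|
| L = 10%, randomised men at L | 0.85 | 0.99 | 1.00 |
| L = 20%, randomised men at 0.5L | 0.03 | 0.23 | 0.67 |

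In the first row the expected pooled rates are 14%, 18% and 22%.

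**3. Would any excess in STAND do as a replacement trigger?** With equal true rates in two arms of 40, the probability that STAND shows more affected men than usual care is 0.43 at a true rate of 10% and 0.44 at 17.5%, at a single look. That is as poor as the no-harm row above.

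**4. Would a formal between-arm test do?** For a doubling from 5, 10, 20 or 30% with 40 per arm, power at two-sided 0.05 is about 0.13, 0.24, 0.50 and 0.78. A by-arm table would inform judgement but would not be a sensitive test.

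**The case against.** A reader might infer that the trigger cannot detect STAND harm at all. The documents do not support that. The clause refers to the study as a whole, so a STAND excess raises the rate, and a doubling of a background at the label rate fires it with probability 0.73-1.00.

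A reader might also infer that STAND harm goes unmonitored. It does not. Grade 2 and higher events are listed for DSMC review, and Grade 3-5 events are recorded and discussed monthly without regard to attribution. A fall or cardiac event during exercise should be seen as a case. What is missing is any arrangement of those cases by arm.

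Three further limits stand:

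- **No product is named.** That LHRH labelling is the reference is an inference from Section 6.1.3. A brochure fits better the investigational agents allowed in Section 4.1, and if chemotherapy labelling were applied to the pilot men, the false-alarm point would weaken.
- **Text directly after the trigger was removed before review.** It cannot be said that this is the plan's only rate rule.
- **The stakes are moderate.** The trigger sends a report and does not stop the study. Each STAND man has four sessions with the exercise trainer over 12 months, and usual-care men can use the same service on request (Section 3.1).

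These points limit the size of the concern. They do not supply a comparison between arms.

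**Conclusion.** The concern holds in a limited form. In the text available, the rate trigger is tied to labelling that does not exist for the randomised intervention and has no arm or cohort split. It is therefore not designed to detect STAND harm and cannot separate it from drug, disease or chemotherapy events.

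How often it would miss an excess depends on background relative to the label. For a doubling under STAND, the firing probability is 0.04-0.18 if background is half the label rate and 0.73-1.00 if background equals it. Chemotherapy toxicity can fire it without any STAND effect, provided an LHRH insert is the reference.

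These figures rest on assumed rates, a per-man reading of frequency, pooling across the study and a single look. The structural point does not depend on them. This is a gap in how safety data are organised, not an absence of safety monitoring, and it is worth correcting because the correction is cheap.

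**What to change.** In Appendix 6, supplement or replace the label comparison as follows:

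- **Table by arm.** Give the DSMC, at its scheduled reviews, a table of the already captured Grade 3-5 events by randomised arm. Show separately the events elicited at the 3-monthly visits common to both arms, because STAND men are also seen monthly and could report more events for that reason alone.
- **Pilot cohort apart.** Tabulate the chemohormonal cohort on its own.
- **Attribution.** Record attribution to STAND components (exercise, nutrition, symptom management) separately from attribution to LHRH therapy.
- **No automatic trigger on any excess.** Leave interpretation of the table to the DSMC, or pre-specify a margin.

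The cost is revised wording in Appendix 6, one attribution field and a routine table. No extra visits or procedures are needed. The downside is that, with 40 men per arm, some chance imbalances will appear and the DSMC will have to weigh them.

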Appendix 7. Specimen Handling and Storage

At baseline, for patients who agree to participate in this optional component of the study, a 12-mL blood sample in two plastic EDTA tubes will be collected from each participant. Samples will be stored in a 80 degrees below Celsius freezer in the UCSF Helen Diller Family Comprehensive Cancer Center. Genomic DNA will be extracted by using a QIAmp DNA Mini Kit () according to the UCSF DNA Bank standard operating procedures. Batched DNA samples will be taken to the [name] laboratory at UCSF Mission Bay campus for polymorphism assessment.

In addition, at baseline and after every 3 months on study, and at 6 months following completion of STAND clinic participation, 20 mL of whole blood will be collected in one tigertop (serum) and one lavender top tube (plasma) and centrifuged at 3000 rpm for 10 minutes. The serum and plasma will be decanted into two 2-mL polypropylene screw cap (leak-proof) vials (four total vials) that have been properly labeled with the unique specimen log number and stored at -80 degrees Celsius.

Samples will be catalogued individually in password protected tissue database. Patient identifiers will be removed from this database and substituted with study ID numbers. Annotations for individual tissue/blood samples will be made for processing.
